## 5.1.2.2 Initial Dosing Following Baseline Visit

Following administration of the first dose, each subject will begin taking an initial daily dosage (# of capsules per day) that is individualized. These subject-specific initial dosages are derived from several factors that were identified (upon analysis of SURE-PD data) as predictors of the daily dosage required to achieve serum urate elevation into a specified range. Factors associated with larger increases in serum urate for a given dose were a) higher screening serum urate levels, b) female gender, and c) diuretic use. Upon randomization of a subject the DCC will automatically send site staff an initial daily dosage plan individualized to the subject (along with an enrollment number and study drug kit assignment). The initial daily dosage plan will be one of five (labeled by letters A to E in Table 4) with two stages. The first stage will employ a relatively low starting dosage for 1 week (through day 6 after BL; BL = day 0), before increasing the daily dosage one week after the BL visit (per schedule in Table 4), except that subjects who are on Plan A will stay on 1 capsule/day after day 6.

Table 4: Initial daily dosage (capsules/day)					
Plan	Day 0 (Baseline)	Day 1 - 6	Day 7 +		
A	1 at visit only	1	1 (no change)		
В	1 at visit only	1	2		
C	1 at visit + 1 at dinner time	2	3		
D	1 at visit + 1 at dinner time	2	4		
E	1 at visit + 1 at dinner time	3	5		

During this initial dosing period (starting on Day 1) and throughout the study the daily dosing schedule will be determined by total daily capsule (cap) dosage as described in Table 5. Following the initial dosing period subjects will remain on the same daily dosage, as tolerated, until a dose adjustment is triggered in response to serum urate measured in blood drawn at subsequent visits (see below).

Table 5: Daily dosing schedule based on total daily capsule count				
caps/day	Breakfast time	Lunch time	Dinner time	
1	1	-	-	
2	1	-	1	
3	1	1	1	
4	1	1	2	
5	2	1	2	
6	2	2	2	

Unless otherwise indicated by the results of inosine-food interaction studies, doses will be organized by approximate mealtimes as subjects are instructed to initially take doses with meals to reduce any risk of dyspepsia. Dose times may vary but consecutive doses should be maintained at least 4 hours apart.

At study visits on treatment (V01-V09) subjects will hold their dose(s) until after the blood draw for trough serum urate sampling, when they will promptly take their first dose of the day. Any subsequent doses for that day will be distributed across the remainder of the day (i.e., with all the day's doses delayed rather than skipped; e.g., for a subject taking at least 3 capsules/day, and therefore on a t.i.d. schedule, who undergoes a visit blood draw at 11 AM s/he will then take the first dose of the day [with fluids during the visit], then the second dose at ~dinner time, and then the third/final dose before bed). A normal dosing schedule will be resumed the following day.

At the discretion of the Investigator, the administration of any two-capsule dose of study drug (i.e., for subjects taking 4 or more caps/day) may be split if it were associated with a minor AE that does not warrant dose reduction. If a two-capsule dose is split then the  $2^{nd}$  capsule may be taken after any delay as long as it is taken at least 4 hours ahead of the next dose.

## **5.1.2.3** Study Drug Dosage Titration Algorithms

A titration algorithm will be employed to lower inosine dosing for over-range levels (>8.0 mg/dL) as well as to increase inosine dosing for those that are under 7.1 mg/dL. A parallel titration algorithm for dosing of subjects on placebo will be used to match their daily capsule dosage to that of subjects on active drug. The resultant adjustments in study drug dosage will be made after each on-treatment visit via person-to-person phone call (or receipt-confirmed forms of email, text message, voice message, etc) from staff to subject within 3 days of receiving a dose adjustment notification from the DCC. At the visits subjects will be instructed to continue their current dosing unless they receive a call (or are otherwise contacted if they mutually agree to an alternative means of communication). When staff contact a subject electronically or otherwise leave a message, the staff must receive from subjects an acknowledgement of receipt of the message and a plan to initiate the change at a specific time and date. Contact will normally only be made when a dose adjustment is warranted, or if a test result warrants a dose change/suspension or other intervention (such as a urine alkalinization).

The Site Investigator and Coordinator will be contacted with instructions by the DCC (by automated email) that will indicate what the study drug dosing should now be and whether this is a change. When subjects are then contacted they should be instructed of the/any dose change and that it should be put into effect immediately (at their next dose). All post-visit contacts, their timing and outcome should be logged in the subject's source documents and the Dose Management Log electronic Case Report Form (eCRF) updated appropriately if a dose adjustment is ordered.

Specific dose adjustments will be made in response to serum urate results at on-treatment visits V01 to V09 (and at any unscheduled on treatment) as follows:

## Subjects randomized to active drug:

- Serum urate < 67% increase from baseline level (calculated as average of SC1, SC2 and BL visit values) to lower limit of target range (7.1 mg/dL) ==> increase by 2 caps/day, except:
  - If subject is already on 5 caps/day, then increase by 1 cap/day up to 6 caps/day.
  - If subject is already on 6 caps/day (possible only after V01) then continue at this dose.
- Serum urate 67-99% increase from baseline level to lower limit of target range ==> increase by 1 cap/day, except:
  - If subject is already at 6 caps/day then continue at this dose.
- Serum urate within target range ==> no change.
- O Serum urate >upper limit of target range (8.0 mg/dL) and  $\leq$  9.0 mg/dL ==> reduce by 1 cap/day the dose being taken at the most recent visit (unless the subject was already down to 1 cap/day in which case s/he will continue at 1 cap/day).
- Serum urate > 9.0 mg/dL ==> hold treatment (i.e., take 0 caps/day) x 6 days, and then resume treatment at 1 less cap/day than the prior dose (i.e., at the most recent visit), except:
  - If that reduction results in no caps being taken, then continue the hold (i.e., 0 caps/day) x 6 more days, then resume treatment at 1 cap/day and return for an unscheduled visit (e.g., U01) in 4 weeks, employing the same titration study drug adjustment algorithm as presented here (Sec. 5.1.2.3) after the unscheduled visit labs are received.
  - If a subject returns 3 consecutive serum urate levels > 9.0 mg/dL on 1 cap/day, then the study drug will be permanently discontinued due to "excess sensitivity to study drug" (not an AE).

## Subjects randomized to placebo:

To preserve blinding to treatment assignment study drug titration will be according to the same titration schedule used for active subjects, but those titrations will be based on a hypothetical serum urate (SU) level calculated as an adjustment from the placebo subject's observed SU level at any given time point. The adjustment will initially be a fixed increment calculated as a function of the subject's current placebo dose. After accumulating some experience with how actual inosine doses affect both mean SU levels and among-subject variation in SU levels, then the increment calculation may be adjusted. Thus the system is designed with the additional flexibility to include some degree of variation among subjects and a nonconstant effect of inosine over time. The following algorithm will be used:

- 1. For placebo subject i at visit j: hypothetical SU[ij] = observed SU[ij] + (U[i] + v[j] + w[ij]) \* # of placebo capsules in current dose.
- 2.  $U[i] \sim Normal(mean S, variance T)$ ; S will be a function of gender, baseline SU, and diuretic use or other participant characteristics; initially T = 0, later T may be greater than 0 based on accumulating data in the trial.
- 3. Initially v[j] = 0 and w[ij] = 0; later v[j] or w[ij] may differ from 0 in order to best match placebo pill counts to those required for titration of participants in the active arm.

#### 5.1.2.4 Missed Doses

The subject should not take a double dose to make up for a missed dose. If a subject forgets to take a particular dose, it should not be made up with the next scheduled dose. Subjects may take a forgotten dose as long as the delayed dose is taken at least 1 hour before the next regularly scheduled dose.

#### 5.1.2.5 Dose Reductions/Suspensions

#### A. Dose Reductions

In addition to serum urate-triggered algorithmic dose reductions (See 5.1.2.3), placebo and active drug may also be reduced during the study if a subject develops a persistent AE that the Enrolling Investigator believes warrants a study drug reduction. Non-Investigator-approved dose reductions may be retroactively assessed and determined to be appropriate by the Site Investigator, for example a dose reduction initiated by another physician upon the subject's hospitalization for an AE.

The duration of the decrement should be the minimum period required to ensure subject safety and comfort. Whether or not the Investigator or another clinician initiates an AE-triggered dose reduction, the Site Investigator should follow the subject as closely as reasonable during the dose reduction period to ensure a prompt re-challenge when appropriate (see Section 5.1.2.6). If an AE-triggered dose reduction or suspension (see 5.1.2.5.B1) is sufficiently long, study drug will be deemed "intolerable" as part of the key trial assessment of tolerability (see Section 10.2.2.2).

The extent of the decrement is at the discretion of the Investigator, and can range from reducing a specific dose (e.g., halving or eliminating the last dose of the day) to eliminating all doses (effectively 'dose suspension'; see 5.1.2.5.B1).

Clinician-initiated dose reductions and their duration are to be recorded on the Dose Management Log and reported to the CCC within 24 hours of initiation. In the event that an AE-triggered dose reduction of any type lasts longer than 72 hours, then the Site Coordinator or Investigator is to contact the Medical Safety Monitor or CCC Project Manager to discuss the situation and review management options.

- **B. Dose Suspensions** may be AE-triggered, precautionary or logistical as follows:
  - 1. AE-triggered suspensions As for AE-triggered dose reductions, AE-triggered suspensions may contribute to a determination that the study drug is intolerable (see Section 12.4.2).
    - a. Automatic:
      - Myocardial or cerebral infarct (If confirmed, drug will be permanently discontinued. See Sections 7.5.1 and 9.0)
      - Gout attack (suspend at least until acute symptoms resolve)
      - Uric acid or urate urolithiasis (suspend at least until any acute symptoms resolve)
    - b. *Investigator-initiated*: as above in 5.1.2.5.A.
  - 2. Precautionary suspensions Investigators may approve a brief non-AE-triggered suspension of study drug employed as a medical precaution (e.g., as in a peri-operative suspension of study drug required by the subject's surgeon for an elective procedure, during a day of potential dehydration as in religious fasting, etc).
  - 3. Logistical suspensions Brief interruptions in study drug use may be incurred due to unavailability (e.g., as in inadvertent destruction, or loss during travel). Re-supply and resumption should occur as soon as possible.

All dose suspensions are to be recorded on the Dose Management Log and reported to the CCC within 24 hours of initiation. In the event that an AE-triggered suspension of any type lasts longer than 72 hours, then the Site Coordinator or Investigator is to contact the Medical Safety Monitor or CCC Project Manager to discuss the situation and review management options.

## 5.1.2.6 Dose Re-challenge and Resumption

Subjects whose dose has been suspended for precautionary or logistical purposes (see Section 5.1.2.5B2 and 5.1.2.5B3) should resume drug as soon as the precautionary or logistical concerns have been adequately addressed. They should resume drug at the level being taken at the time of the suspension.

Subjects whose dose has been reduced or suspended due to an adverse effect (see Sections 5.1.2.5A and 5.1.2.5B1) must tolerate the reduced or suspended drug level for two or more full days (i.e., equal to or greater than 48 hours) before being re-challenged. After this time the re-challenge may begin with a partially or fully resumed dose of the study drug (i.e., the dose being taken at the time of reduction or suspension). Whether the re-challenge is immediately at the full dosage (i.e., resumption) or gradually escalating is at the discretion of the Site Investigator. Re-challenge and resumption should be pursued with expedience while ensuring the subject's likely safety and comfort. If the AE recurs as the dosage is increased, the subject should continue on the maximally tolerated dosage up to the full dose.

All dose re-challenges and resumptions are to be recorded on the Dose Management Log and reported to the CCC within 24 hours of initiation. Having to back down on the dosage during a re-challenge is considered another dose reduction and should be reported to the CCC as such and recorded on the Dose Management Log.

Note that persistent dosing below the full study drug regimen (as dictated by serum urate-titrated dosing plan; Section 5.1.2.3) would lead to a determination that the intended dose was "intolerable" as per Section 10.2.2.2.

#### 5.1.2.7 Question of Need for Downward Titration

There is no downward titration necessary when study drug is reduced, suspended temporarily, or permanently discontinued.

# 5.1.3 Potential Adverse Effects (AEs) of Study Drug

## **5.1.3.1 Potential AEs of Active Drug (Inosine)**

Anticipated AEs of inosine are expected to be primarily mediated by urate, to which it is rapidly metabolized. Established AEs of elevating urate are disorders of crystallization, as reviewed above. The two main disorders are gout (a form of arthritis triggered by urate crystals forming in a joint) and uric acid urolithiasis (uric acid crystalizing at low urine pH to form stones). Although gout is often a progressive degenerative arthritis, any inosine-induced episodes of acute gouty arthritis would be expected to be fully reversible upon discontinuation of inosine and thus would not require additional medication. Similarly urolithiasis is often a recurrent nephropathic disease, whereas uric acid stones induced by inosine would not be expected to recur if inosine were discontinued. Nevertheless the study incorporates numerous safeguards against these conditions, particularly uric acid urolithiasis given our phase 2 data indicating that a small but significant portion of the study cohort may develop stones. (See Sec. 2.2.3.)

In addition, as surveyed above in Sec. 2, numerous other medical conditions have been linked to higher serum urate and include cardiovascular diseases, including hypertension, coronary artery disease, heart failure, stroke, and renal dysfunction, and metabolic disorders (metabolic syndrome and diabetes mellitus). Although it remains uncertain whether or not urate itself contributes to these conditions and their increased risk with higher urate is generally modest, special attention will be paid to both avoiding and monitoring for these conditions during the trial.

## **5.1.3.2 Potential AEs of Placebo (Lactose)**

No specific AEs of placebo drug are anticipated. Note that symptoms due to lactose intolerance (a theoretically placebo-specific potential AE) are unlikely given that the maximum single dose of 1 gm lactose (two 0.5 gm placebo capsules) is well below the limit of lactose sensitivity (typically >12 gm/serving) in lactose-intolerant people. 179,180 By comparison, 50 gm lactose is considered the standard challenge dose in lactose intolerance tests.

# 5.2 Handling of Study Medications

Study drug will be manufactured in the same opaque white, hard gelatin capsules for both placebo and active drug formulations. Their indistinguishable appearance will be confirmed initially after manufacturing and at least annually thereafter during the study through a scheduled stability testing program. Study drug will be packaged with 100 capsules per bottle, which will be white high-density polyethylene (HDPE) with a standard lid closure. All study drug formulation, encapsulation and bulk packaging (into bottles) will be conducted by a single contract manufacturer.

Study drug will undergo final packing, labeling and distribution to clinical sites by a central pharmacy. Six study drug bottles of placebo or active drug will be assembled into a kit box and labeled to meet applicable US regulatory requirements. Each kit box is good for at least 3 months of dosing. Each subject

who completes the study without early drug discontinuation will receive from 2 to 8 kit boxes (12 to 48 bottles) in total depending on the dose level maintained.

The central pharmacy will label and supply subject kits for each study center according to the randomization list provided by the project DCC Biostatistics Core. Each kit and its bottles will be identified via a 5-digit Enrollment ID Number as defined by this randomization list to maintain study blindedness. Pre-assigned start-up study drug kits will be supplied to the Site Investigator once Institutional Review Board (IRB)/Independent Ethics Committee (IEC) approval is granted and all regulatory documents are filed and contractual arrangements are in place. Additional start-up kits will be provided by the central pharmacy as site enrollment warrants. The central pharmacy will send additional supplies for a given enrolled subject in advance of each dispensing visit.

In accordance with local regulatory requirements, the Site Investigator or designated site staff must document the amount of investigational product dispensed and/or administered to study subjects, the amount received from the central pharmacy, and the amount destroyed upon completion of the study. The Site Investigator is responsible for ensuring product accountability records are maintained throughout the course of the study. The inventory will include details of the study drug and dispensed to subjects, batch, and ID numbers. All unused capsules and bottles must be kept until reconciliation of delivery records with accountability logs by the monitor. Subjects will be asked to maintain a daily drug diary to confirm drug was taken as prescribed. After the monitor has performed accountability, the site will be instructed by the CCC or designee to either destroy the remaining study medication per institutional policy or return it to the central pharmacy. An accounting must be made of any drug deliberately or accidentally destroyed. Discrepancies between the amount of study drug received and dispensed drug must be reconciled.

# 5.3 Concomitant Medications

## **5.3.1** Required Therapy

There is no required therapy to take on a regular basis in addition to study drug. Subjects with persistently acidic urine will be prescribed potassium citrate (or an alternative medication) as a urine alkalinization method to reduce the risk of uric acid stone formation. See Sec. 8.4.2.

#### **5.3.2** Prohibited Medications

## **5.3.2.1** Disallowed Medications Prior to Study Entry

Subjects who have used certain medications as specified under the study exclusion criteria (Sec. 4.2) will not be eligible for participation in this study.

#### **5.3.2.2** Disallowed Medications during the Study

Use of the following medications is not allowed during the study. The use of any disallowed medication must be documented.

- Multivitamins and/or mineral preparations, other than a standard daily multivitamin\*.
- Antioxidants such as vitamin E, vitamin C and inosine (other than as may be in study drug, a standard daily multivitamin or a normal diet)\*
- Neuroleptics (typical and atypical), metoclopramide
- Methylphenidate, amphetamine, cinnarizine, reserpine, tetrabenazine, MAO-A inhibitors, or appetite suppressants\*
- The urate-reducing agents, allopurinol, febuxostat and probenecid.

\*Please see Section 18, Concomitant Medications, in the site Manual of Procedures located on the study ePortal section: for further details related to these disallowed medications.

#### **5.3.3** Allowed Concomitant Medications

All concomitant medications that the subject is taking at study initiation must be recorded on the Concomitant Medication Log. The log will include a list of all medications taken during the 30-day period prior to the 2nd Screening Visit. Any changes in concomitant medications or new medications added, including use with an intercurrent illness, must be recorded in the case report forms. All concomitant medications must be used in accordance with approved labeling and as prescribed.

## **5.3.3.1** Initiation of Antiparkinsonian Medication

Although anti-PD medications other than monoamine oxidase B inhibitors are not permitted at entry, anti-PD medications may be initiated during the study. The decision to initiate antiparkinsonian treatment must be made by the Site Investigator at an in-person visit (regular or unscheduled), and only after a determination that the subject has developed the need for dopaminergic therapy. For this study 'dopaminergic therapy' is defined as symptomatic treatment with an antiparkinsonian drug (levodopa, a dopamine agonist, amantadine or an anticholinergic agent trihexyphenidyl or benztropine), other than a MAO-B inhibitor taken at enrollment. Increasing an entry dosage of a MAO-B inhibitor or initiating a MAO-B inhibitor during the study will be considered as requiring dopaminergic therapy. Once treatment has been initiated, dosage adjustments may be ordered by telephone. Dosing of a monoamine oxidase B inhibitor that was taken at enrollment should remain unaltered until (additional) dopaminergic therapy is initiated or until the subject's final study visit.

# 5.3.3.2 Initiation of Thiazide Therapy during the Study

Initiation of treatment with a prescription thiazide -- such as hydrochlorothiazide (e.g., Esidrex), chlorothiazide (e.g., Diuril), chlorthalidone (e.g., Hygroton), indapamide (e.g., Lozol), metolazone (e.g., Zaroxolyn) -- will be allowed. However, thiazide therapy can cause an increase in serum urate (usually <1 mg/dL). Accordingly, a regular or unscheduled visit with serum urate measurement by the central lab must occur between 1 and 4 weeks after initiation of any thiazide to afford timely algorithmic adjustment of study drug dosing. Although diets can also influence serum urate,  they are generally stable and any changes are expected to prompt titration of study drug dosing based on placebo and inosine dosing algorithms.

# **5.4** Adherence Assessments

At each study visit, the Site Investigator and/or Study Coordinator will assess the subject's compliance with the study requirements. This will include checks of protocol compliance, concomitant medication use, and use of study drug in order to assess the reliability of subject-generated data. The primary mechanism for assessing compliance with use of study drug will be capsule counts i.e., the number of capsules dispensed and returned at each visit will be documented in the Study Drug Dispensing/Return Log. Subjects are instructed to return all study bottles (whether empty, partially used, or unused) at each visit on study drug (V01-V09) and upon its discontinuation (V10).

Non-compliance will be defined as taking less than 80% or more than 125% of study medication as determined by capsule counts. If a study subject is non-compliant with study medication, the Site Investigator and staff should re-educate and train the subject in administration of study drug. Subjects who fail to comply with the study requirements may be withdrawn from the study. Data indicating non-compliance will be used in the end of study analysis, when they may be related to pharmacodynamic evidence of non-compliance (e.g., lack of increase in serum urate on maximum inosine dosage).

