## 9. CRITERIA FOR DRUG DISCONTINUATION AND SUBJECT WITHDRAWAL

Subjects will be advised in the written informed consent forms that they have the right to permanently discontinue study drug and/or withdraw from the study at any time without prejudice, and may be withdrawn from drug and/or the study at the discretion of the Site Investigator, CCC Director and/or Study Principal Investigator at any time. Subjects who prematurely discontinue study drug will be asked to continue study participation via in-person visits if willing, and otherwise via quarterly telephone visits. Some premature drug discontinuations and/or study withdrawals may be unavoidable, but the Site Coordinator and Site Investigator will work closely with the study CCC, Medical Safety Monitor and Study Principal Investigator to attempt to retain subjects, if appropriate. See Sections 7.5 to 7.6 for further discussion of non-standard visits for drug or visit discontinuation and premature withdrawal.

Every effort should be made to obtain the subject's final laboratory tests and evaluations of clinical status. Reasonable effort should be made to contact any subject lost to follow-up during the course of the study in order to complete assessments and retrieve any outstanding data, drugs or clinical supplies. In this case, the Site Investigator must use reasonable effort to contact the subject in order to finalize study-related procedures. Following unsuccessful telephone contact, an effort to contact the subject by mail using a method that provides proof of receipt, should be attempted. Such efforts should be documented in the source documents.

A subject may discontinue study drug and/or withdraw from the study and/or be withdrawn from drug and/or the study for the following reasons:

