## **Administrative**

- 1. Withdrawal of subject consent
- 2. Request of Site Investigator or Study Principal Investigator
- 3. Request of primary care physician
- 4. Non-compliance
- 5. Pregnancy (Study drug will be discontinued in the event of a pregnancy, and every reasonable effort should be made to assess the health of the mother/fetus during the pregnancy and its outcome.)
- 6. Protocol deviation
- 7. Premature termination of the study

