## 10.1.3 Analysis Samples

A modified intention-to-treat (mITT) sample will include all randomized subjects who received at least one dose of study drug, each classified according to their randomized treatment assignment without regard to compliance with their assigned treatment. An as-treated (AT) sample will include all subjects who received at least one dose of study drug classified according to the actual treatment received and reclassifying subjects randomized to inosine who report not taking inosine and reclassifying subjects randomized to placebo who report taking inosine or whose serum urate during treatment averages 6.5 mg/dL or greater (note: no such subjects out of 25 randomized to placebo were observed in SURE-PD). Separate analysis will also look only at intervals on study drug, censoring follow-up after study drug discontinuation, and at serum urate elevation as achieved, distinct from either randomized or self-selected treatment as administered.

The primary efficacy analyses will use the mITT sample to best estimate the expected effectiveness of urate-elevating oral inosine supplementation in clinical practice, recognizing that compliance in clinical use may differ from compliance in the clinical trial. Analyses of tolerance will also use the mITT sample. Analyses of safety will use the AT sample to avoid downwardly biased estimates of adverse outcomes associated with inosine exposure due to treatment non-compliance. Secondary analyses of efficacy outcomes will also use the AT sample to perhaps better estimate efficacy of inosine supplementation as administered and serum urate elevation as achieved.

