6.2 Analysis Samples

The following analysis samples will be used for testing effectiveness, efficacy, safety, and tolerability endpoints:

- Intent-to-treat (ITT) Sample: Participants who are randomized, classified according to their randomized treatment assignment. Participants determined to have been ineligible prior to randomization, participants who never initiate study drug, and observations made after premature permanent discontinuation of study drug are included in this sample.
- As-treated (AT) Sample: Participants who are eligible, randomized, and take at least one dose of study drug. If a participant permanently discontinues study drug, observations made during period 1 will be censored following the first visit after study drug discontinuation. Separate analyses will classify participants in the AT sample either according to the actual treatment received or according to the average post-baseline serum urate concentration achieved. Participants randomized to inosine who report not taking inosine will be reclassified as placebo participants. Participants randomized to placebo who report taking inosine or whose serum urate during treatment averages 6.5 mg/dL or greater will be reclassified as inosine participants.

• Safety and Tolerability (ST) Sample: Participants who are randomized and take at least one dose of study drug, classified according to the actual treatment received. Participants determined to have been ineligible prior to randomization and observations made after premature permanent discontinuation of study drug are included in this sample.

The primary efficacy analyses will use the ITT sample to best estimate the expected effectiveness of urate-elevating oral inosine supplementation in clinical practice, recognizing that compliance in clinical use may differ from compliance in the clinical trial. Secondary analyses of efficacy outcomes will use the AT sample to best estimate efficacy of inosine supplementation as administered and serum urate elevation as achieved. Analyses of safety and tolerance will use the ST sample.

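### Protocol 5.4 and Section 9 let non-compliant participants be withdrawn from the whole study, so follow-up that the ITT analysis is built to use can be lost avoidably

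*Protocol*

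**What the plan says.** Protocol 5.4 sets a capsule-count definition: "Non-compliance will be defined as taking less than 80% or more than 125% of study medication as determined by capsule counts". The stated response is to re-educate and retrain the participant. The section then adds that "Subjects who fail to comply with the study requirements may be withdrawn from the study". The object is the study, not study drug.

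Protocol Section 9 repeats the power: participants "may be withdrawn from drug and/or the study at the discretion of the Site Investigator", and the same sentence gives it also to the coordinating-center director and the study's principal investigator. The Administrative list of reasons includes "Non-compliance" and protocol deviation, under a lead-in that covers stopping drug, leaving the study, or both.

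The analysis plan points the other way. Protocol 10.1.3 defines its mITT sample with participants "each classified according to their randomized treatment assignment without regard to compliance with their assigned treatment". SAP 6.2, which is authoritative on analysis, uses an ITT sample of everyone randomized, includes observations made after permanent drug discontinuation, and justifies this by "recognizing that compliance in clinical use may differ from compliance in the clinical trial". SAP 6.6.4 (Disability Warranting Dopaminergic Therapy) notes that follow-up continues in people who have stopped study drug.

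**The concern.** Compliance is measured after randomization. If a participant's adherence falls and the participant is then removed from the study, the later off-drug or low-dose course is never observed. That course is what separates an ITT estimate from an estimate in compliers. The primary mixed model then has to project it from earlier visits under missing at random (SAP 6.6.11).

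Three other analyses are touched:
- Time to disability loses later events.
- The comparison after wash-out is described as covering all those randomized (SAP 2.1).
- Tolerance requires remaining on study (SAP 4.6), so an administrative withdrawal could count as intolerance.

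The rule has no criteria beyond staff discretion and may be applied differently across about 60 sites.

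**Working it through.** **1. Does any provision keep the follow-up?**

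| Provision | Covers | Covers withdrawal from the study? |
|---|---|---|
| Protocol 9, retention: "Subjects who prematurely discontinue study drug will be asked to continue study participation via in-person visits if willing", otherwise by telephone | Stopping drug | No |
| Protocol 7.5.3, telephone visits | Stopping in-person visits; collects AEs, medications and need for dopaminergic therapy | No, and no MDS-UPDRS |
| Protocol 7.6, premature withdrawal | Separates stopping drug from leaving the study | Defines it; does not prevent it |
| Protocol 8.7, AE follow-up | 30 days after premature withdrawal, if the participant is willing | Brief safety follow-up only |
| SAP 6.6.11, placebo-based multiple imputation | Missing primary-endpoint data | Models the data; does not collect them |

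None keeps a participant in MDS-UPDRS follow-up after withdrawal from the study for non-compliance.

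**2. Reproduce the plan's power (SAP 3.8).** Inputs: 135 per arm, effect 6.3/24 = 0.2625 units/month, SD 0.76, two-sided alpha 0.046 (critical value 1.995).
- SE = 0.76 × √(2/135) = 0.0925
- z = 0.2625/0.0925 = 2.838
- Power = Φ(2.838 − 1.995) = 80.0%, and the required total is 270, as stated.
- With the unrounded SD of 0.758, power is 80.2%. Steps 3 and 4 start from this figure.

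**3. Withdrawals spread over time.** The documents give no rate, so 5% and 10% over 24 months, beyond the loss allowance, are assumptions. The effective SD was recalculated from a shared-baseline random-slopes information matrix with:
- the SAP 3.8 subject-level components (intercept 77.4, slope 0.230, covariance 2.87, residual 13.9);
- the planned visits;
- assumed exponential censoring totalling 70% + 8% = 78% at 24 months, plus the extra withdrawal.

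Site effects were omitted and the censoring shape was assumed, so the starting SD is 0.557 against the stated 0.587. The result is therefore used only as a ratio to scale 0.758.
- 5%: SD 0.7655, power 79.4%, N for 80% power 274
- 10%: SD 0.7749, power 78.5%, N 282

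**4. Worst case: all data from withdrawn participants lost.**
- 5%: 135 × 0.95 = 128.25 per arm, power 78.2%, N = 270/0.95 = 285 (rounded up)
- 10%: 135 × 0.90 = 121.5 per arm, power 75.9%, N = 270/0.90 = 300

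**5. Upper bound on bias.** Suppose 5% of the inosine arm are non-compliant and gain nothing, while the rest gain Δ. The ITT effect is 0.95Δ. Removing those participants entirely gives Δ, a ratio of 1/0.95 = 1.053, or about 5% too large. Visits before withdrawal stay in the model, including visits made while non-compliant, so the real overstatement under these assumptions would be smaller.

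**The case against.** The strongest reply is that the text is permissive and may never have been used. Several points support it:
- Re-education comes first, and 5.4 goes on to say that non-compliance data will be used in the final analysis.
- The one worked example, in Protocol 8.8 on overdose, treats non-compliance as a reason for stopping drug only.
- Section 9 asks staff to try to retain participants and to obtain final evaluations, and the discontinuation visit in 7.5.2 includes MDS-UPDRS.
- Phase 2 completion was 99% (Protocol 2.2.3).
- The 8% loss allowance may already include such withdrawals.
- About 70% of participants are expected to be censored at dopaminergic therapy under the same missing-data assumption, so a few more withdrawals add little. Visits after that point are outside the primary analysis anyway.

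All of this stands, and it limits the size of the problem. It does not supply follow-up for anyone withdrawn from the study.

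Two stronger readings are tempting, and the documents support neither. A reader might infer that the ITT sample excludes non-compliers or discards their data. It does not: SAP 6.2 keeps everyone randomized, and only visits after withdrawal are lost. The conflict is one of purpose, not of definition. A reader might also infer that the MDS-UPDRS rater alone can remove participants with knowledge of treatment. Section 9 shares the discretion with central staff, SAP 2.7 keeps site investigators blinded, and Protocol 7.2.2 withholds serum urate results from sites from Baseline on. A link between withdrawal and arm, for example through tolerability, is possible but not shown.

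**Conclusion.** The concern holds in limited form. The protocol permits withdrawal from the study for non-compliance or protocol deviation, and no provision preserves follow-up when that is done. This undercuts the purpose of the SAP's ITT analysis and the continued follow-up assumed in SAP 6.6.4. Placebo-based imputation softens the problem but does not replace data that could be collected.

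The stated N and power are not in dispute. At the assumed extra rates of 5% and 10%, the power loss is under two points when withdrawals are spread over time. The figures of about 78% and 76% are worst cases, and the 5% overstatement of effect is an upper bound, not an estimate. Actual use of the rule is unknown and may be close to zero. What makes it worth correcting is that this adherence-dependent missingness is avoidable at little cost.

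**What to change.** In Protocol 5.4 and Section 9, state that non-compliance or a protocol deviation alone does not end study participation. Participants continue scheduled in-person visits where willing, with telephone visits as the fallback, through Month 27 unless they withdraw consent or are lost to follow-up. In-person visits should be preferred, because telephone visits collect no MDS-UPDRS. Whether study drug is stopped is a separate decision and is left as it stands.

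The change adds no visits to the schedule. Its cost is a protocol amendment, which under Protocol 12.4 needs approval by the principal investigator, the Steering Committee and each site's IRB.

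The SAP records that sites were notified of early closeout on 25 Oct 2018. If follow-up is already complete, an amendment recovers nothing. In that case, report the number withdrawn for non-compliance or protocol deviation by arm within the disposition summary of SAP 6.8.1, which already presents reasons for withdrawal.
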